### **Compliance measures, side effects and adverse events**

Compliance to randomization, allocation and interventions, and drop outs are reported (**Fig 1, Table 2**). Total fluid volume was identical at inception but both groups showed a reduction compared to baseline at time-2. However, as per the trial design, the study group showed significantly (all  $p < 0.05$ ) lower volume intake, feeding in right side lying position, and postprandial supine position. Feeding duration of actual feeding was increased in the study group but not statistically different from the conventional group. No side effects or adverse events were reported in either group.

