## **STUDY INTERVENTIONS**

### **Interventions**

Providers employ uniform feeding and nutritional practices in our NICU infants as per our standardized guidelines, which applies to nutrient and volume modifications. However, upon randomization and allocation, individual protocols are complied with. Upon completion of screening, enrollment and randomization, the assigned feeding management strategy was relayed to parents and the medical team. Subjects in both arms received omeprazole off label, as a therapeutic choice (27, 28) at a recommended dose of 0.75 mg/kg/dose BID (15, 27, 29). The conventional approach was to not adjust provider recommended feeding strategies (i.e. fed in any

position, duration, volume, and postprandial position). The study approach utilized a modified feeding strategy including: a) feeding in the right lateral position to facilitate intra-prandial gastric emptying (30), b) feeding duration of at least 30 min utilizing pacing when orally fed to ensure completion of prescribed volumes or via pump to ensure steady delivery of milk if gavage-fed (21), c) supine postprandial position (31), and d) limiting total feeding volume to  $\leq 140$  ml/kg/day (21).

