*Salient features of our study include:* 1) Allocations were unbiased and appropriately distributed between groups. 2) Among those presenting with GERD symptoms at inception, about 36% of infants had normal esophageal acid exposure, while 40% had abnormal acid exposure, and the rest in the indeterminate range. 3) The study bundle was not superior to acid suppression alone in improving primary outcomes or secondary outcomes. 4) Restricted feeding volume, body positions (intra- and post-prandial), oral or gavage feeding methods, supplemental oxygen, birth gestation and postnatal maturation did not influence the primary or secondary outcomes. 5) Reliability of compliance among those discharged was based on parental trust and available information. 6) There were no reported adverse events. No differences in long term developmental outcomes or economic burden measures, such as, LOHS, feeding methods and respiratory support at discharge were noted. 7) Symptom scores (I-GERQ-R) were significantly lower in both groups, suggesting that maturation may play a role in symptom modification, and not the bundled approaches. 8) Feeding outcomes improved in both groups.

*GMT Trial strengths and clinical implications are several:* 1) Random allocation, study design and protocol adherence were robust and rigorous. Although our strict inclusion criteria may have led to lower eligibility, our approach resulted in identifying infants carefully with true ARI as a marker of esophageal acid exposure. Objective determination of GERD based on ARI >7%

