## **CONCLUSION**

We addressed the current practice controversies in this clinical trial: 1) Screening and identifying acid-GERD objectively is possible in symptomatic infants prior to any pharmacotherapy. 2) Feeding strategy modification (fluid restriction, positional changes, prolonged feeding duration) has no role in decreasing reflux-type symptoms or in improving the primary outcome of achieving independent oral feeds and/or a six-point decrease in I-GERQ-R score. 3) No difference in the prevalence of chronic lung disease was noted between the groups. 4) I-GERQ-R scores decreased across time regardless of treatment group allocations that strongly

support maturational effect. However, we did not detect an effect on *a priori* short-term or long-term outcomes following randomized allocations. As restrictive feeding strategies do not make a difference, placebo-controlled clinical trials in a larger cohort of convalescing NICU infants with objectively determined newer GERD criteria must be addressed in future trials.

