**Table 2. Primary and Secondary Clinical Outcomes and Compliance Measures**

Primary Outcome (intent-to-treat analysis)	Overall (N = 76)	Conventional (N = 36)	Study (N = 40)	P-value
A priori clinical outcome Success, n (%)	29 (38)	16 (44)	13 (33)	0.28
Secondary Outcomes	Overall (N = 72)	Conventional (N = 35)	Study (N = 37)	P-value
I-GERQ-R decrease by 6 – n (%)	24/65 (37)	11/31 (35)	13/34 (38)	0.82
Feeding Outcome at Time 2 – n (%)				0.26
PO	51 (71)	27 (77)	24 (65)	
Transition (PO + Tube)	18 (25)	8 (23)	10 (27)	
Tube	3 (4)	0 (0)	3 (8)	
Length of hospital stay – days	108 [82 - 128]	108 [83 - 125]	98 [81 - 132]	0.89
Hospital stay Inception to Discharge – days	25 [11 - 45]	23 [3 - 39]	27 [16 - 47]	0.26
Weight Growth Velocity (GV) – g/day	27.1 (9.4)	26.5 (7.2)	27.6 (11.1)	0.64
Length GV – cm/day*	0.1 (0.1)	0.1 (0.1)	0.1 (0.1)	0.88
Head Circumference GV – cm/day*	0.1 [0.0 - 0.1]	0.1 [0.0 - 0.1]	0.1 [0.0 - 0.1]	0.87
Feeding Method at Discharge – n (%)				0.32
PO	54 (75)	29 (83)	25 (68)	
Transition (PO + Tube)	14 (19)	5 (14)	9 (24)	
Tube	4 (6)	1 (3)	3 (8)	
Oxygen Requirement at discharge – n (%)	16 (22)	9 (26)	7 (19)	0.49
Compliance to Feeding Methods				
Total Fluid Volume (TFV)				
TFV at Inception- #	N/A	150 [147, 152]	150 [149, 156]	0.8
TFV at Time 2- #	N/A	143 [134, 148]*	133 [126, 137]*	<0.001
# days TFV ≤ 140 / kg / day	N/A	10 [2, 26]	22 [11, 31]	0.005
TFV compliance (TFV <140/kg/d for >75% of time)	N/A	9 (26)	27 (73)	<0.001
Position				
Feeding Position, RSL, %	N/A	5 [1, 17]	78 [12, 94]	<0.001
Feeding in RSL >75% of the time, %	N/A	0 (0)	21 (57)	<0.001
Supine Position Post-Prandial, %	N/A	50 [40, 66]	87 [74, 96]	<0.001
Supine Position Post-prandial >75% of the time, %	N/A	7/34 (21)	27/36 (75)	<0.001
Feeding Duration				
% time feed duration >30 min, %	N/A	4 [0, 37]	15 [0, 69]	0.15
Feeding Duration at Inception, min	N/A	23 [17, 41]	30 [19, 34]	0.64
Feeding Duration at Time 2, min	N/A	23 [18, 28]	26 [20, 30]	0.15
Long-term Follow-up†				
Feeding Method at 6 months – n (%)				0.65
PO	36/50 (72)	21/27 (78)	15/23 (65)	
Transition (PO + Tube)	10/50 (20)	4/27 (15)	6/23 (26)	
Tube	4/50 (8)	2/27 (7)	2/23 (9)	
Feeding Method at 1 year – n (%)				0.11
PO	37/44 (84)	20/22 (91)	17/22 (77)	
Transition (PO + Tube)	4/44 (9)	0/22 (0)	4/22 (18)	
Tube	3/44 (7)	2/22 (9)	1/22 (5)	
CCABSID-III				
Cognitive Score <80 – n (%)	9/44 (21)	5/23 (22)	4/21 (19)	1.00
Cognitive Score – #	95 [90 - 105]	100 [90 - 105]	90 [90 - 100]	0.11

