## **5.0 Study Intervention/Investigational Agent**

- Those subjects randomized into the study group will follow innovative feeding strategy for 5 weeks. The innovative feeding strategy is as follows:
  - Feeding Volume  $\leq$ 140 ml/kg/d
  - Feeding duration over 30 minutes
  - Right lateral feeding position
  - Supine position postprandial

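### Prolonged feeding duration was not delivered to most study infants, so the conclusion that it has no role is unsupported and the adherence claims do not fit Table 2

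*Combined protocol and SAP*

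**What the plan says.** Duration is one of four components of the study bundle. The Interventions section assigns a "feeding duration of at least 30 min", and the protocol's Study Summary (section 1.0) agrees. Protocol section 5.0 states it as "Feeding duration over 30 minutes". Table 2 scores it in a row for the percentage of "time feed duration >30 min".

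The results section on compliance lists significant separation for volume, feeding position and postprandial position. On duration it says: "Feeding duration of actual feeding was increased in the study group but not statistically different from the conventional group".

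The Conclusion nevertheless states: "Feeding strategy modification (fluid restriction, positional changes, prolonged feeding duration) has no role in decreasing reflux-type symptoms". Among the strengths, the Discussion says "Random allocation, study design and protocol adherence were robust and rigorous", and its next item describes treatment as delivered uniformly in the two groups. The limitations paragraph does not mention duration.

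**The concern.** A null result for a bundle informs us about a component only to the extent that the arms differed on that component. Here the Conclusion names prolonged duration among the modifications without a role, while the compliance data suggest that most study infants did not receive it.

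Duration was also part of the reason for the trial. The Introduction and protocol section 3.2 cite the group's earlier observational finding that longer feeding went with fewer reflux events. A reader of the Conclusion would take that hypothesis as tested and rejected. A reader of the strengths paragraph would take the null result as applying to the full four-part bundle.

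**Working it through.** All inputs are from Table 2. I take 35 conventional and 37 study infants for the duration rows, as in the secondary-outcome column heads. This is an assumption, because those rows print no denominators.

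**Step 1. Reproduce the printed compliance shares (>75% of the time).** Pearson chi-square without continuity correction:

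| Component | Study | Conventional | p |
|---|---|---|---|
| Volume | 27/37 = 73.0% | 9/35 = 25.7% | 0.00006 |
| Right-side feeding | 21/37 = 56.8% | 0/35 = 0% | <0.000001 |
| Supine postprandial | 27/36 = 75.0% | 7/34 = 20.6% | 0.000005 |

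All agree with the printed percentages and p<0.001. Duration has no such row.

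**Step 2. Bound duration on the same threshold.** The per-infant share of time with feeds over 30 min has an upper quartile of 69% in the study arm. Since 69 < 75, no more than about 25% of infants can lie above 75%: 0.25 × 37 = 9.25, or about 9 infants. The same ceiling applies to meeting all four components together. In the other direction, about a quarter of study infants had feeds over 30 min for at least 69% of the time.

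**Step 3. Durations in minutes, median [IQR].**

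| | Study | Conventional | Printed p |
|---|---|---|---|
| Inception | 30 [19, 34] | 23 [17, 41] | 0.64 |
| Time 2 | 26 [20, 30] | 23 [18, 28] | 0.15 |
| Change in arm median | 26 − 30 = −4 | 23 − 23 = 0 | not given |

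At Time 2 at least half of the study infants were at or below 26 min, and about three quarters were at or below 30 min. The results text's statement that duration increased holds only between arms at Time 2. Within the study arm the median fell. The −4 is a difference of two medians, not a median of paired changes.

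**Step 4. Rough size of the Time-2 contrast.** With SD ≈ IQR/1.349, each arm has SD ≈ 10/1.349 = 7.41.

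- SE = 7.41 × √(1/35 + 1/37) ≈ 1.75
- Difference in medians = 26 − 23 = 3 min
- Approximate 95% interval = 3 ± 1.96 × 1.75 = −0.4 to 6.4 min
- Approximate p = 0.09; the printed value is 0.15

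This is a normal approximation from quartiles and serves only to show scale. It should not be used for the inception row, where the quartiles are skewed: there it gives p ≈ 0.05 against the printed 0.64.

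**Step 5. Sensitivity to the 30-minute boundary.** The Table 2 row excludes feeds of exactly 30 min. Under the Interventions wording those feeds comply, so the 15% and the Step 2 ceiling could both rise. The documents do not allow a bound on how much. The Time-2 median of 26 min is below 30 under either wording.

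**The case against.** The strongest reply is that the Conclusion speaks of the bundle. Its grammatical subject is the strategy as a whole, and the parenthesis lists what was randomized. The hypothesis and the abstract are also at bundle level, and the intention-to-treat comparison of the assigned strategies is valid whatever the adherence. Where the Discussion lists individual factors without influence, it names volume and positions but not duration. Three of four components separated at p<0.001, the results text discloses that the fourth did not, and no adherence threshold was set in advance for calling delivery robust.

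Much of this stands. The primary comparison is untouched, and duration belongs in any description of the assigned arm. But the Conclusion claims that the listed modifications have no role, which goes beyond saying that the assigned package was not superior. Disclosure in the results does not correct a conclusion and a strengths paragraph that read otherwise, or its absence from the limitations.

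A reader might go further and infer four things that the documents do not support:

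- **That the data contradict the conclusion.** Nothing in them shows that longer feeds help. The no-role statement is unsupported, which is weaker than refuted.
- **That duration was not delivered at all.** About a quarter of study infants had long feeds most of the time.
- **That the arms did not differ, so there is no information.** A p-value of 0.15 does not show equality, and the rough interval reaches 6.4 min.
- **That the Table 2 row is mis-scored.** Its cut-off matches protocol section 5.0. The fault is that the documents carry two definitions.

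**Conclusion.** The point holds as an issue of reporting and interpretation. Duration did not clearly separate the arms (a 3-minute difference in Time-2 medians), and most study infants were below 30 min at Time 2. On the threshold used for the other components, about a quarter or fewer could have complied on duration, against 73%, 57% and 75%. The trial gives very little information about prolonged duration, and the statement that it has no role is unsupported.

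The statements on robust adherence and uniform delivery do not fit Table 2. Duration is the clearest case. They are weakened further by right-side feeding at 57% and by the 26% of conventional infants who also met the volume criterion.

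The compliance ceiling assumes the over-30 scoring in Table 2 and quartiles based on about 37 infants. The Time-2 medians need neither assumption.

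**What to change.** 1. Limit the Conclusion to the bundle as delivered, for example:

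> Assignment to the bundle, as delivered, was not superior to acid suppression alone. Feeding duration differed little between arms, and these data do not show that prolonged duration is without effect.

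2. Add the limited delivery of the duration component to the limitations.
3. In the strengths paragraph, replace the wording on robust adherence and uniform delivery with the adherence figures for all four components in both arms, including duration on the same >75%-of-time threshold.
4. Reconcile the two statements of the duration requirement (Interventions and protocol section 1.0 against protocol section 5.0), then score the Table 2 row to the reconciled definition. Which definition applies is for the investigators to state.

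The cost is wording, one added adherence row, and possibly one re-scored row from feeding data already collected. The primary and secondary outcome analyses do not change.

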### **DISCUSSION**

In this RCT, while controlling for birth gestation and severity of acidity, we compared the effectiveness of acid suppression with or without a systematic feeding modification bundle in modifying feeding outcomes and I-GERQ-R scores. We found no differences in our *a priori* primary outcome or pre-assigned secondary outcomes. Important clinical and research implications can be noted despite the non-superiority of the feeding bundle.

Diagnostic conundrums and management issues with GERD in the NICU setting persist. Prior studies (8, 19, 20) used perceived clinical symptoms as a basis for acid-suppression, but studies have shown lack of benefit on symptom improvement (35, 36). Recent work by us (6, 21, 22), suggests that such symptoms are often due to pharyngo-esophageal provocation or cross-systems activation of reflexes, and can occur during non-acid events or swallowing events, or

during transient relaxation of lower esophageal sphincter (30). However, the inability to handle the refluxate determines the ‘troublesomeness of the symptoms’ rather than the esophageal acid exposure. Clinical practice varies when pathophysiological reasoning is not commonly applied. Clinical practices can have unintended consequences (1, 37-40) resulting from acid suppression, undernutrition, delays with feeding milestones, decisional conflicts, discharge outcomes and prolonged hospitalization, all of which can escalate burden (9, 27).

*Salient features of our study include:* 1) Allocations were unbiased and appropriately distributed between groups. 2) Among those presenting with GERD symptoms at inception, about 36% of infants had normal esophageal acid exposure, while 40% had abnormal acid exposure, and the rest in the indeterminate range. 3) The study bundle was not superior to acid suppression alone in improving primary outcomes or secondary outcomes. 4) Restricted feeding volume, body positions (intra- and post-prandial), oral or gavage feeding methods, supplemental oxygen, birth gestation and postnatal maturation did not influence the primary or secondary outcomes. 5) Reliability of compliance among those discharged was based on parental trust and available information. 6) There were no reported adverse events. No differences in long term developmental outcomes or economic burden measures, such as, LOHS, feeding methods and respiratory support at discharge were noted. 7) Symptom scores (I-GERQ-R) were significantly lower in both groups, suggesting that maturation may play a role in symptom modification, and not the bundled approaches. 8) Feeding outcomes improved in both groups.

*GMT Trial strengths and clinical implications are several:* 1) Random allocation, study design and protocol adherence were robust and rigorous. Although our strict inclusion criteria may have led to lower eligibility, our approach resulted in identifying infants carefully with true ARI as a marker of esophageal acid exposure. Objective determination of GERD based on ARI >7%

is justifiable in future trials, as nearly 40% of infants are in this severe range, and it is possible to study such a group in larger clinical trials based on pH and impedance criteria, while employing placebo for equipoise. Since time-limited PPI therapy concurrent with feeding strategies was neither shown to be beneficial or associated with adverse effects, we believe that, it is safe to include a completely untreated placebo group in future trials that enroll patients with objectively determined acid-GERD. 2) The management strategies were tightly regulated, as were feeding and testing guidelines, and the treatment was uniformly delivered across the two groups. The patient population was homogeneous and constituted a fair representation from the convalescing NICU population. In addition, the randomized controlled allocation accounted for premature or full-term birth, and the indeterminate or determinate acid-GERD per ARI. Furthermore, the prevalence of oxygen requirement or tube feeding at discharge was not different between groups. 3) Our study trial has many elements of objectivity. Determination of I-GERQ-R and ARI, as well as monitoring feeding methods during the trial are strengths. Thirty-six percent of those with aerodigestive and or cardiorespiratory symptoms perceived by their clinicians to be due to GERD prior to trial consent, were not randomized and were also never treated with a PPI as the esophageal acid exposure was normal (ARI < 3%). In a purely symptom-based clinical trial, all those 688 infants screened would have likely been treated for presumed GERD. In the current study, only those that had true ARI exposure have been randomized and treated. Therefore, the symptom-based approach alone is not the solution to diagnose and treat GERD. Interestingly, perception of symptoms (IGERQR scores) decreased across time regardless of treatment group allocations (**Fig 2**). These findings strongly support maturational effect. As both groups were treated with PPI, placebo-included RCTs are needed to determine if maturation alone will improve objectively determined acid- and non-acid-GERD. 4) Absence of pH-impedance testing to confirm true acid-GERD prior

to randomization would have resulted in all patients being treated based on subjective, non-specific symptoms alone. Owing to the strict inclusion and exclusion criteria of this RCT, those with indeterminate and abnormal ARI were treated with a PPI. In the future, a careful RCT that tests the utility of PPI treatment for confirmed acid-GERD by allocating patients to either limited PPI treatment or placebo is indicated to determine whether PPI treatment is needed. The effectiveness of our short-term use of PPI for 4 weeks to improve GERD-attributable symptoms should be tested in future trials. Effect of esophageal acid exposure and therapies on primary mechanistic outcomes of esophageal motility and symptom causation will be addressed in future reports. 5) In routine clinical practice, feeding volumes are modified and alterations in feeding positions are used to manage symptoms. Our study did not show any differences in the outcomes with feeding- and position modifications. Furthermore, volume restriction had no influence on the study outcomes. The improvement in symptoms and feeding outcomes over time irrespective of PPI or feeding modifications may suggest a maturational effect.

It is important to note that major mechanisms of GER, i.e. transient LES relaxation is the major reason for any reflux events- both acid or non-acid substrate. Our therapeutic target was acid reflux index in this study via PPI, feeding volumes, and positional changes. Given that acid GER can also have weakly or non-acid either before or after PPI therapy, and that there were no differences in outcomes between the two groups, we speculate that neither PPI, feeding volume, or positional changes modify the studied indices or symptoms. Maturation under optimal conditions of good nutrition along with placebo-controlled trials are needed to answer the importance of weakly acid or non-acid GER, which would require a multicenter trial with a large group of infants with appropriate physiologic diagnostic testing.

*Our study has limitations.* 1) Parental and physician biases appeared to be a barrier to recruitment. Recruitment was slow despite the high prevalence of GERD-associated symptoms and a high eligibility rate. This is concerning, as many parents refused clinical trial participation. Many infants did not have true acid-GERD, and fluid restriction often occurred before testing. Interestingly, in some cases, parents and providers did not want to stop the PPI use. These barriers to recruitment can be mitigated in future larger trials with better parent-provider education, as no major effects on the primary or secondary outcomes were noted in our study with or without our allocated bundled GERD treatment. 2) Owing to the higher screening to eligibility ratio, rigorous inclusion criteria, and strict study protocols, we could not complete the recruitment as originally planned of 100 evaluable patients. Seventy-six infants were randomly assigned during the funding period. However, using this cumulative sample size of 72 patients for interim monitoring, we found that we would stop for futility at this time point even if the funding period was not ended. 3) Further studies are needed to correlate parental/provider perception of symptoms (I-GERQ-R) with true symptoms and symptom indices examined during pH-impedance testing. Such studies should also address the severity of acid exposure index in relation to changes in symptom indices.

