## STUDY OUTCOMES

### Primary and Secondary Clinical Outcomes

The clinically meaningful primary and secondary outcomes did not differ significantly between groups (**Table 2**). I-GERQ-R scores for study and conventional groups are shown (**Fig 2**). At inception: positive I-GERQ-R was 19/35 (54%) in the conventional group vs 24/37 (65%) in the study group,  $p=0.36$ . At Time-2: positive I-GERQ-R prevalence was 9/31 (29%) in the conventional group vs 13/34 (38%) in the study group,  $p=0.43$ . In the study group vs conventional group, respectively: a) primary outcome achieved in 33% (95% CI, 19% - 49%) vs 44% (95% CI, 28% - 62%) ( $p=0.28$ ), b) secondary outcomes: independent oral feeding in 65% (95% CI, 48% - 80%) vs 77% (95% CI, 60% - 90%),  $p=0.26$ ,  $\geq 6$ -point I-GERQ-R decrease in 38% (95% CI, 22% - 56%) vs 35% (95% CI, 19% - 55%),  $p=0.82$ , length of stay was 98 [81-132] days vs 108 [83-125] days,  $p=0.89$ , and oxygen requirement at discharge in 19% (95% CI, 8% - 35%) vs 26% (95% CI, 13% - 43%),  $p=0.49$ . There were no significant differences in growth metrics (all  $p>0.05$ ) or developmental scores at 2 years (all  $p>0.05$ ). Feeding outcomes or I-GERQ-R scores did not significantly differ between conventional vs study groups based on feeding method at inception (**Table 3**). Individual I-GERQ-R questions relating to vomiting, regurgitation, and crying (i.e. frequency of emesis, volume of emesis, symptoms with emesis, and crying more than usual in the

past week) had no differences ( $P>0.05$ ) within the group or between the groups across maturation for these individual symptoms, except for symptoms with emesis (never: rarely: sometimes: often: always, %) was 16:16:42:19:6 for conventional group at Time-1 vs 18:18:29:0:35 for study group at Time-1,  $p < 0.01$ .

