- Sample Size Determination:
  - From the more recent preliminary data analysis, 83.3% (20/24, 95% CI: 62.6%-95.2%) of patients had success based on symptoms and feeding methods in the innovative strategy group, while only 35% (7/20, 95% CI: 15.4%-59.2%) had success in the standard therapy group. In order to provide greater assurance than afforded by comparing to historical control of the standard therapy, a total of evaluable 100 patients will be randomized into the innovative feeding strategy or standard therapy group. The chi- square test yields 80% power to detect 27% or higher increase in proportion of success while maintaining an overall one-sided  $\alpha$  level of 0.025. This conservative power calculation is supported by the preliminary data and assumes the proportion of success for the standard therapy is around 40% and a group-sequential design with O’Brien-Fleming error spending function.
- Interim Analysis:

- One interim futility analysis will be undertaken at about 50% information prior to the final analysis at 100% information, corresponding to 50 and 100 evaluable patients, respectively. The boundary is determined using Lan-DeMets spending functions to simulate O'Brien-Fleming boundaries with an overall one-sided  $\alpha$  level of 0.025. Using the target proportion of success, the boundary at the futility analysis expressed as a p-value is 0.297. We plan to enroll 120 patients to allow for 20% of attrition.
- Intention to treat analysis:

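### Non-significant secondary-outcome tests are reported as no effect without any between-arm interval, although the data exclude neither important harm nor important benefit

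*Combined protocol and SAP*

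**What the plan says.** The Results (Primary and Secondary Clinical Outcomes) dispose of two-year development in one phrase: "developmental scores at 2 years (all $p>0.05". That section gives 95% intervals for some binary outcomes, but only within each arm.

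The null tests are then carried forward in increasingly firm language:

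- Discussion, salient features, item 6: "No differences in long term developmental outcomes or economic burden measures, such as, LOHS, feeding methods and respiratory support at discharge were noted". Item 4 of the same list says that volume, position and other factors did not influence the primary or secondary outcomes.
- Discussion, strengths, item 2: "the prevalence of oxygen requirement or tube feeding at discharge was not different between groups". Item 5 says volume restriction had no influence on the outcomes.
- Discussion, limitations, item 1, on overcoming reluctance to enrol: "as no major effects on the primary or secondary outcomes were noted in our study with or without our allocated bundled GERD treatment".
- Key Points and the closing sentence of the Conclusion both say, without qualification, that restrictive feeding has no impact or makes no difference.

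More careful wording also appears. The Abstract concludes that the bundle is not superior, and the Conclusion says at one point that no effect was detected.

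For Aim 1, protocol section 3.3 gives a power figure for the primary endpoint only: "80% power to detect 27% or higher increase in proportion of success while maintaining an overall one-sided" alpha of 0.025. It gives no effect size, margin or power for the Bayley or feeding-method outcomes.

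**The concern.** A test that fails to reach p<0.05 supports a statement of no effect only if the interval around the difference is narrow enough to exclude effects that matter. The reader cannot judge this here, because no between-arm interval is printed. The long-term outcomes also rest on roughly a third to just over a half of the randomized infants.

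The direction matters in both senses. The bundle lowers intake, and Table 2 shows that it did so (median 133 vs 143 at Time 2). The Discussion itself lists undernutrition and delayed feeding milestones among the possible unintended consequences of clinical practice. Development and oral feeding are therefore outcomes on which a reader will look for cost as well as gain. The limitations section uses the null result as reassurance for future parents and providers. If the data cannot bear that weight, the trial is being used to settle a question that it left open.

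**Working it through.** **Plan's own figure.** Inputs from section 3.3: 50 evaluable infants per arm, control success "assumes the proportion of success for the standard therapy is around 40% and a group-sequential design" (so 40% vs 67%), one-sided 0.025. Power = Φ{[0.27√50 − 1.96√(2×0.535×0.465)] / √(0.40×0.60 + 0.67×0.33)} = Φ{(1.909 − 1.383)/0.679} = 78.1%. This is close to the stated 80%, but it concerns the primary endpoint only.

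**Reported p-values.** The Table 2 feeding p-values reproduce with the exact test on three categories: 0.26 at Time 2, 0.32 at discharge, 0.65 at 6 months, 0.11 at 1 year. The Bayley below-80 p-values also reproduce (1.00, 0.83, 0.69, 0.49). The published tests are not in dispute.

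**Power for Bayley scores.** Arm sizes are from Table 2. Difference = 0.5 SD (assumed). Two-sided 5% (assumed, since the statistical methods give only P<0.05). Noncentrality = 0.5/√(1/n₁+1/n₂). Interval half-width in SD units = t₀.₉₇₅ × √(1/n₁+1/n₂).

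| Scale | Conventional, study | Share of 76 | Power | 95% CI half-width |
|---|---|---|---|---|
| Cognitive | 23, 21 | 58% | 37% | 0.61 SD |
| Receptive | 23, 19 | 55% | 35% | 0.63 SD |
| Expressive | 14, 11 | 33% | 22% | 0.83 SD |
| Fine motor | 23, 18 | 54% | 34% | 0.64 SD |

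The chance of missing a 0.5-SD difference is thus 63% to 78%. A normal approximation gives 62% to 76%, and Wilcoxon efficiency gives 65% to 79%. The difference detectable with 80% power runs from 0.87 SD (cognitive) to 1.18 SD (expressive). About 63 scored infants per arm would be needed for 0.5 SD.

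**Not fully orally fed (partial plus exclusive tube), study minus conventional, Newcombe 95% CI.** Worked case, discharge: 12/37 = 0.324 (Wilson 0.196 to 0.485) and 6/35 = 0.171 (0.081 to 0.327). The difference is 0.153. Lower limit = 0.153 − √[(0.324−0.196)² + (0.327−0.171)²] ≈ −0.05. Upper limit = 0.153 + √[(0.485−0.324)² + (0.171−0.081)²] ≈ +0.34.

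| Time | Study | Conventional | Difference (points) | 95% CI |
|---|---|---|---|---|
| Time 2 | 13/37 | 8/35 | +12 | −9 to +32 |
| Discharge | 12/37 | 6/35 | +15 | −5 to +34 |
| 6 months | 8/23 | 6/27 | +13 | −12 to +36 |
| 1 year | 5/22 | 2/22 | +14 | −9 to +35 |

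**Outcomes that lean the other way or are mixed.**

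- Bayley below 80, study minus conventional, in points: cognitive −3 (−26 to +22), receptive −3 (−29 to +24), expressive −14 (−45 to +23), fine motor +12 (−15 to +38). The first three lean towards the bundle.
- Weight velocity, 27.6 (11.1) study, n=37, vs 26.5 (7.2) conventional, n=35: pooled SD = √[(36×11.1² + 34×7.2²)/70] = 9.4; SE = 9.4√(1/37+1/35) = 2.2; difference +1.1 g/day, 95% CI about −3.3 to +5.5.
- Oxygen at discharge, 7/37 vs 9/35: −7 points (−26 to +12).

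**Limits of reconstruction.** Score differences cannot be recovered reliably from medians and quartiles. For fine motor (97 [82-110] vs 88 [70-97]) an approximate mean difference is −11. With an SD taken from the quartiles the interval is −24 to +2. With an assumed SD of 15 it is −21 to −2, which excludes zero and conflicts with the reported p=0.13. The cognitive row, "95 [90 - 105] 100 [90 - 105] 90 [90 - 100] 0.11", has a study-arm median equal to its lower quartile, so a normal approximation is doubtful there too. Patient-level data are needed.

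**The case against.** A reader might infer that the report formally clears the bundle of harm, or claims non-inferiority. It does not. The quoted sentence in item 6 says only that differences were not noted, the secondary outcomes sit under a superiority hypothesis, and nowhere does the report say that volume restriction carries no developmental or feeding cost. It argues against using the bundle, so nobody is being steered towards it. The remark on major effects concerns recruitment barriers, and the sentence on unintended consequences is about clinical practice in general. All of this stands. It limits the point to wording and missing intervals.

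A reader might also infer from the feeding rows that the bundle did harm. The documents do not support that:

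- The four comparisons are repeated looks at overlapping infants, and every interval includes zero.
- Both fully gavage-fed infants at inception were in the study arm, and the lower quartile of oral intake there was 22 vs 57 mL/kg/day (Table 1).
- Among infants orally fed at inception, 17/17 study and 16/17 conventional stayed so (Table 3).
- Exclusive tube feeding at 1 year was 1/22 study vs 2/22 conventional.
- Growth, the most direct measure of undernutrition, does not lean against the bundle.

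It is also fair that the report prints per-arm intervals for some outcomes, and that the Table 2 footnote discloses incomplete follow-up. Neither gives the reader the precision of a between-arm difference. The limitations section mentions the recruitment shortfall, but not the low precision or the missing long-term data.

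**Conclusion.** The point holds as one about inference and reporting. The secondary-outcome data are compatible with a clinically important cost and with a clinically important gain from the bundle, so the absolute no-effect statements are not supported. For feeding, the intervals reach 32 to 36 more infants per 100 not fully orally fed, and also 5 to 12 fewer. For development, half-widths of 0.61 to 0.83 SD leave differences of more than half an SD open on every scale, even if the observed difference were zero.

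This rests on a 0.5-SD benchmark with no source in the documents, on two-sided 5% testing, and on complete-case denominators from Table 2. The interval results do not depend on the benchmark. Nothing here shows that harm occurred, and nothing in the report amounts to a formal claim that harm was ruled out.

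**What to change.** 1. From patient-level data, report the study-minus-conventional difference with its 95% interval for every secondary outcome: growth velocities, length of stay, oxygen at discharge, each Bayley score and below-80 rate, and feeding method at Time 2, discharge, 6 months and 1 year. Show partial and exclusive tube feeding separately. Give the share of randomized infants followed beside each.
2. In the Key Points, the Results on clinical outcomes, the Discussion (salient features items 4 and 6, strengths items 2 and 5) and the Conclusion, replace the absolute wording with: *no difference was detected; differences within the reported intervals cannot be excluded*.
3. In limitations item 1, remove the use of the null result as reassurance about recruitment.
4. Add a limitation stating the low precision and the missing long-term follow-up.
5. Do not write a harm margin into protocol section 3.3. The data were locked in May 2019, so any margin chosen now must be labelled post hoc. With these half-widths, a 0.5-SD margin could not be excluded at an observed difference of zero.

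The cost is a short analysis of data already held, some rewording, and a less reassuring conclusion.
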